7.5 Vital signs and body weight

Each summary will include only scheduled assessments (re-test excluded) and listings will include both scheduled and unscheduled assessments.

The change from baseline (baseline as defined in Section 11.4) to Visit 3 (Week 14), Visit 4 (Week 27), Visit 5 (Week 40) and the run-out period Visit 6 (Week 41) in vital signs (systolic and diastolic blood pressure, and pulse rate) will be summarized. The observed values at baseline and each scheduled post-baseline visit will also be summarized.

The change from baseline (baseline as defined in Section 11.4) to Visit 5 (Week 40; or last value on study) in body weight will be summarized.

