7 SAFETY VARIABLES AND ANALYSES

7.1 Overview of safety analyses including subgroup analyses

Unless noted otherwise, the SS will be used for tables and listings of safety data. Safety data described below will be listed.

In the event of permanent study treatment discontinuation, it is recommended per protocol to perform the safety assessments of Visit 5 within 7 days of the last double-blind study treatment intake. Although some subjects may be considered as being off study treatment, the time from the last double-blind study treatment intake to the Visit 5 assessments is expected to be short. Therefore, for subjects who prematurely discontinue treatment, the safety data (laboratory tests, ECG, vital signs) measured within 7 days of the last double-blind study treatment intake will be included as being taken during double-blind study treatment. A subject who prematurely discontinues treatment may continue the planned study visits until EOS, without the run-out period. Therefore, for subjects who prematurely discontinue treatment, the safety data (laboratory tests, ECG, vital signs) measured more than 7 days from the last double-blind study treatment intake will be excluded from analyses.

Any unscheduled or re-test measurements will be excluded for determining last values during the double-blind treatment period. All scheduled, re-test and unscheduled measurements will be included for determining baseline values.

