11.2 Study periods

The enrollment period is defined as the time from the informed consent date until one day before double-blind study treatment start date.

The double-blind study period is defined as the time from the day of double-blind study treatment start until the day of EODBT (Visit 5) or for those who prematurely discontinued double-blind study treatment (i.e., those without an EODBT date), until one day after double-blind study treatment end date (if the treatment is taken before midnight), or the day of double-blind study treatment end date (if the treatment is taken after midnight). Time of treatment intake between 00:00 and 11:59 is considered as 'after midnight', while a time between 12:00 and 23:59 is considered as 'before midnight'. For any missing or incomplete time, it is presumed that the treatment was taken before midnight. For subjects lost to follow-up, the EOS date will be used as the end of DB study treatment. For subjects who complete double-blind study treatment with an interruption before continuing the run-out single-blind placebo treatment, the end of double-blind study period is the run-out

single-blind placebo treatment start date – 1 day. For subjects who prematurely discontinue treatment, the safety data (laboratory tests, ECG and vital signs) assessment up to 7 days after last drug intake are considered in the definition of double-blind study period [see Section 7.1].

For those subjects in the TWS, the treatment withdrawal period (or the run-out period) is defined as the time from one day after the end of the double-blind study period to the latter of seven days after the end of the double-blind study period or Visit 6 date. If the latter of the two dates falls after the EOS date, then the EOS date will be used.

The safety follow-up period is defined as the time from one day after the end of the treatment withdrawal period for those starting the treatment withdrawal period (i.e., subjects in the TWS) until the EOS date; or from one day after the end of double-blind study period for those not starting the treatment withdrawal period until the EOS date.

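### The body-weight summary in SAP 7.5 sets no limit relative to last dose, while the SAP's 7-day rule for early stoppers does not name body weight

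*SAP*

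**What the plan says.** SAP Section 7.5 gives body weight a single summary, the change from baseline to Visit 5 at Week 40, with the alternative "or last value on study) in body weight will be summarized". The section uses scheduled assessments only and does not relate the weight to the date of last intake.

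For subjects who discontinue treatment early, Section 7.1 treats laboratory, ECG and vital-sign data within 7 days of last double-blind intake as on treatment. Data of those types "measured more than 7 days from the last double-blind study treatment intake will be excluded from analyses". Section 11.2 carries the same rule into the period definition: "the safety data (laboratory tests, ECG and vital signs) assessment up to 7 days after last drug intake are considered". Body weight appears in neither place.

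Section 7.1 also foresees that these subjects may stay in the study: "A subject who prematurely discontinues treatment may continue the planned study visits until EOS, without the run-out period". On timing, "it is recommended per protocol to perform the safety assessments of Visit 5 within 7 days of the last double-blind study treatment intake".

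Section 11.5 lets a change from baseline use any assessment after baseline up to EOS. Section 7.3 restricts the laboratory last value to the double-blind study period.

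**The concern.** For laboratory, ECG and vital-sign data, the SAP has decided that a value taken more than 7 days after an early stopper's last dose should not be read as an effect of treatment. It makes no such decision for weight. The fallback refers to the study, not to the treatment period, and the general definition of change from baseline does not narrow it.

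Long-term safety is the primary objective, and this is the only weight summary specified. Vital signs are tabulated by visit, but weight has one endpoint, so no by-visit weight table would show which values were taken off drug. If weight changed on treatment and moved back after stopping, off-drug values would pull the group mean towards no change. The documents do not say whether such an effect exists.

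**Working it through.** The plan states no figure to reproduce. The check compares the sections and then does simple calendar arithmetic.

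**Rules side by side**

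| SAP section | Data | Limit for early stoppers |
|---|---|---|
| 7.1 | Laboratory, ECG, vital signs | Excluded if more than 7 days after last intake |
| 11.2 | Laboratory, ECG, vital signs | Counted in the double-blind study period up to 7 days after last intake |
| 7.3 | Laboratory last value | Must fall in the double-blind study period |
| 7.5 | Body weight | None stated |
| 11.5 | Any change from baseline | Any value up to EOS |

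**Does the term vital signs in 7.1 include weight?** Section 7.5 specifies the summary "in vital signs (systolic and diastolic blood pressure, and pulse rate) will be summarized" and gives weight a separate sentence. On that wording, weight falls outside the rule.

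**Does the scheduled-only restriction help?** No. A planned visit attended after stopping is still a scheduled assessment.

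**How can an off-drug weight enter?** There are two routes:
1. The subject has no Visit 5 weight, and the last value on study was taken after stopping.
2. The subject stops early but attends Visit 5 at Week 40. That weight is off drug and is used without any fallback.

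**How long could the gap be?** The documents allow two readings.
- Section 2 places EOS 30 days after the last double-blind dose. If that governs early stoppers, the gap is at most about 30 days, and the excess over the limit is 30 − 7 = 23 days.
- If early stoppers keep the original calendar, the gap is the visit day minus the last-dose day, with Week 14 = Day 98, Week 27 = Day 189 and Week 40 = Day 280. Take a stop at Week 12 (Day 84) as an illustration that is not from the documents. The gaps are 98 − 84 = 14, 189 − 84 = 105 and 280 − 84 = 196 days.

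Either reading can exceed 7 days, and the documents do not settle which applies. They also do not show at which visits weight is measured, because the supplied protocol text is only the COVID-19 addendum. The arithmetic therefore shows what the wording permits and does not estimate what will happen.

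**The case against.** The best reply is that the matter may already be handled. Section 7.5 is titled for vital signs and body weight together, so 7.1 may use vital signs as shorthand for both. Late weights would then already be excluded. That is possible, but 7.5 lists vital signs as blood pressure and pulse rate, and under this reading the fallback to the last value on study would conflict with the exclusion. The text needs a clarification either way.

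A second reply is that weight may be measured after baseline only at Visit 5. The last value on study could then simply be the Visit 5 assessment brought forward at early stopping, which is recommended within 7 days. Most such weights would be close to treatment. The documents cannot rule this out. However, the 7-day timing is a recommendation, and the wording of 7.5 does not depend on it.

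A third reply is that a last observed value regardless of treatment status is a legitimate descriptive choice. That is so, but the SAP does not say it made this choice for weight, and it chose otherwise for the other safety measurements.

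It also stands that early-stopper values kept under the 7-day rule reflect shorter exposure than Week 40. No rule removes that limitation.

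**Conclusion.** The point holds as a gap and an inconsistency in handling, not as a direct contradiction. Read literally, the SAP lets off-drug weights from early stoppers into a summary by actual treatment received, whereas it limits laboratory, ECG and vital-sign data in the same subjects. The consequence is small: one descriptive table, with no test or sample size resting on it. Closing the gap is a cheap improvement.

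Four stronger readings are tempting and are not supported:
- A reader might infer that weights will be taken months after stopping. Section 2 may cap the gap near 30 days, and the weight schedule is not available.
- A reader might infer that a calculable share of the values is off drug and that the mean change is understated by that share. The documents give no discontinuation rate, no share of early stoppers with a later weight and no evidence of reversal.
- A reader might infer that weight and vital signs are taken at the same visits under two rules. Section 7.5 summarises vital signs at Visits 3, 4, 5 and 6 but weight only at Visit 5 or the fallback.
- A reader might infer that the values are attributed to the assigned dose. Under Section 4.1.3, Safety Set summaries use the treatment actually received.

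The conclusion assumes only that 7.5 is applied as worded and that at least some early stoppers have a weight recorded more than 7 days after last intake.

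**What to change.** Make three linked edits:
1. In Sections 7.1 and 11.2, add body weight to the data types under the 7-day rule.
2. In Section 7.5, define the endpoint as *Visit 5 (Week 40), or last scheduled value in the double-blind study period*. State that the 7-day rule applies to the Visit 5 value as well as to the fallback.
3. Show later weights separately, labelled as off-treatment.

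All of these are needed. Changing only the fallback phrase leaves in the Week 40 weight of an early stopper who attends Visit 5. Changing only 7.5 would be too strict: without the 7-day extension, Section 11.2 ends the period for early stoppers no later than one day after the last intake, so a Visit 5 weight taken a few days later would be lost.

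If the sponsor does want all weights on study regardless of treatment, the SAP should say so and the table should be labelled accordingly.

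The cost is a few words in the SAP and no new data collection. A few subjects lose a value from one descriptive table, and the early-stopper values that remain reflect shorter exposure.

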7.6 Withdrawal symptoms

The TWS will be used to assess the potential for withdrawal symptoms.

The BWSQ assesses the main symptoms which might be experienced by subjects during withdrawal from benzodiazepines. The questionnaire consists of 20 items with each item rated by the subject as either 0 (No), 1 (Yes—moderate) to 2 (Yes—severe). The BWSQ total score (possible range: 0–40) for the observed values and change from the last available assessment on double-blind study treatment to the end of the treatment withdrawal period will be summarized. Observed values will also be summarized.

The number and percentage of subjects with a BWSQ total score above 20 will be tabulated by visit. The number and percentage of subjects with one or more BWSQ symptom scored as ‘severe’ will be tabulated by visit.

In addition, withdrawal symptoms after double-blind study treatment discontinuation will be assessed through the incidence of AEs, and marked ECG abnormalities, occurring during the treatment withdrawal period [see Section 11.2]. As described in their respective sections, the incidence of AEs [Section 7.2] and marked ECG abnormalities [Section 7.4] occurring during the treatment withdrawal period (between Visit 5 and Visit 6) will be summarized.

7.7 Rebound insomnia

The TWS will be used to assess the potential for rebound insomnia.

The change from baseline (baseline as defined in Section 6.1) to the treatment withdrawal period (Visit 6, Week 41, see Section 11.7) in the subjective sleep parameter sTST will be summarized using descriptive statistics.

Empirical cumulative distribution function plots of this subjective sleep parameter for each treatment group will be provided together with a summary showing the cumulative number and percentage of subjects meeting certain thresholds for the observed range of values.

7.8 Next-day residual effect

Sheehan Disability Scale[®]

The SDS[®] consists of three questions on impairment of work, social life, and family life / home responsibilities each on a 10-point scale. The three items will be summed into a single dimensional measure of global functional impairment that ranges from 0 (unimpaired) to 30 (highly impaired). Number of days lost (school, work or normal daily responsibilities) and number of days underproductive (school, work or normal daily responsibilities) are also collected and will be summarized.

The change from baseline^a to Visit 3 (Week 14), Visit 4 (Week 27), Visit 5 (Week 40) and run-out period Visit 6 (Week 41) in each SDS[®] item (impairment of work, social life, family life / home responsibilities, number of days lost and number of days underproductive) and Total score will be summarized. The Total score will be calculated only for subjects with all the three items available: impairment of work, social life and family life / home responsibilities. Observed values will also be summarized.

^a For subjects entering ID-078A303 and assigned to the same treatment arm as that of the confirmatory studies (ACT-541468 10 mg, 25 mg, or 50 mg, or placebo), baseline is the mean of the two PSG morning assessments at Visit 3 of the run-in period in the confirmatory study. For subjects entering ID-078A303 who received placebo in the confirmatory studies and who are randomized (switched) to 25 mg of ACT-541468 in the extension study, baseline is as defined in Section 11.4.

Visual Analog Scales

The change from baseline over time (baseline and over time as defined in Section 6.1) in morning sleepiness VAS score will be summarized. Observed values will also be summarized.

7.9 Columbia Suicide Severity Rating Scale[®]

The C-SSRS[®] is an instrument that evaluates suicidal ideation and behaviors.

The C-SSRS[®] outcome categories are provided below. Each category has a binary response (yes/no) and are numbered and ordered for convenience.

1. Wish to be Dead
2. Non-specific Active Suicidal Thoughts
3. Active Suicidal Ideation with Any Methods (Not Plan) without Intent to Act
4. Active Suicidal Ideation with Some Intent to Act, without Specific Plan
5. Active Suicidal Ideation with Specific Plan and Intent
6. Preparatory Acts or Behavior
7. Aborted Attempt
8. Interrupted Attempt
9. Actual Attempt (Non-Fatal)
10. Completed Suicide

Self-injurious behavior without suicidal intent is also a C-SSRS[®] outcome (although not suicide-related) and has a binary response (yes/no).

Categories 1–5 relate to suicidal ideation and a score of 0 is assigned if no suicidal ideation is present. Categories 6–10 relate to suicidal behavior.

Based on the C-SSRS[®], the number and percentage of subjects with suicidal ideation by category, suicidal behavior by category, suicidal ideation or behavior and/or self-injurious behavior without suicidal intent, 1) during the double-blind study period and 2) during the treatment withdrawal period (based on TWS) will be tabulated separately. Percentages will be based on the number of subjects with at least one post-baseline C-SSRS[®] assessment, in the corresponding period. The assessment will be assigned to a study period based on a scheduled visit as follows: V1 (Day 1) = not assigned any study period; V3 (Week 14), V4 (Week 27) and V5 (Week 40) = double-blind study period; V6 (Week 41) = Treatment withdrawal (or Run-out) period.

Shift from baseline (baseline as defined in Section 11.4) showing any change in suicidal ideation and suicidal behavior, 1) during the double-blind study period and 2) during the treatment withdrawal period (based on TWS), will be provided separately. Subjects will be summarized under the worst of the following three categories, shown here in the order from best to worst: 1) No suicidal ideation or behavior, 2) Suicidal ideation, and 3) Suicidal behavior (subjects with both suicidal ideation and suicidal behavior are included in the suicidal behavior category and not in the suicidal ideation category). Suicidal ideation includes any one of the five suicidal ideation events (categories 1–5). Suicidal behavior includes any one of the five suicidal behavior events (categories 6–10).

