**During the telephone call or video call visit [protocol section 7]:**

- The investigator will interview the subject for:
  - Occurrence of any new AEs or worsening of existing ones.

- When asking about the occurrence of AEs, please follow the same process as for a site visit, i.e., use an open-ended question, such as:
  - “Have you had any significant medical problems since the last study visit?”
- Collection of additional information about AESI as applicable. AESI include:
  - Narcolepsy-like symptoms (i.e., EDS, cataplexy and complex sleep behavior events including hallucinations / sleep paralysis),
  - Suicide / self-injury.
- Checking for next day residual effects [see Section 2.4].
- Assessing withdrawal and rebound (only applicable to Visit 6) [see Section 2.4].
- Completion of the C-SSRS questionnaire.
- If closer monitoring of any of the above symptoms is required but not possible, depending on the severity of the symptoms observed and the investigator’s assessment of the benefit-risk for the subject participation in the trial, the investigator can consider discontinuing treatment while trying to maintain the subject in the study [protocol section 5.1.9].
- Changes in any ongoing medication or start of new medication(s).
- Check compliance with study medication and potential overdose or other medication error(s) [protocol sections 5.1.7 and 9.1.1].
- The telephone or video contact must be entered under the visit it replaces (e.g., if the assessments were intended for Visit 3, please use the Visit 3 form) and documented in detail (day, time and conversation) in the subject’s medical charts. All assessments not performed must be entered as “Not done”.
- Should any additional telephone calls be performed to ensure the subject’s safety that are not part of the regular visit plan, the call must be entered as an unscheduled visit (‘UNS’) in the eCRF and documented in detail (day and reason for the ‘UNS’) in the subject’s medical charts.
- For Visit 6 please also refer to Section 2.4

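### SAP 7.9 gives a study period only to C-SSRS ratings from scheduled Visits 3 to 6, so a post-baseline rating filed as unscheduled would enter no C-SSRS table

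*SAP*

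**What the plan says.** SAP Section 7.9 reports C-SSRS outcomes by category for two periods, double-blind and treatment withdrawal. The period comes from the visit label: "The assessment will be assigned to a study period based on a scheduled visit as follows". The list is short: "V1 (Day 1) = not assigned any study period", then "V3 (Week 14), V4 (Week 27) and V5 (Week 40) = double-blind study period; V6 (Week 41) = Treatment withdrawal (or Run-out) period". Unscheduled contacts and Visit 7 are not on it.

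Two other parts of the section depend on that assignment. For the denominator, "Percentages will be based on the number of subjects with at least one post-baseline" C-SSRS assessment in the period concerned. The shift tables are those "showing any change in suicidal ideation and suicidal behavior, 1) during the double-blind study period and 2) during the treatment withdrawal period", using each subject's worst category. Completed suicide is category 10 and belongs to the behavior group: "Suicidal behavior includes any one of the five suicidal behavior events".

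Section 2.2 of the COVID-19 protocol addendum distinguishes two kinds of call. A call that stands in for a planned visit is entered on that visit's form. For extra safety calls "that are not part of the regular visit plan, the call must be entered as an unscheduled visit" (UNS). C-SSRS completion is on the list for the remote visit, and addendum Section 2.4.1.4 asks for it when a call replaces an on-site visit.

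**The concern.** An unscheduled rating is more likely than a routine one to follow from someone's worry about the subject, so it is more likely to be positive. If such ratings have no period, the tables omit the records that matter most, and the error tends towards too few events. Long-term safety is the primary objective (SAP 3.1), suicide/self-injury is an AESI, and Section 10 applies every analysis in the SAP to the interim report for regulatory filings. A C-SSRS table could then show no event in an arm while a positive rating sits only in a listing.

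**Working it through.** The documents give no rate, sample size or precision target for the C-SSRS, so there is no planned figure to reproduce. The check follows each kind of record through the Section 7.9 list.

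| Record | Filed under | Period in 7.9 | In the C-SSRS tables? |
|---|---|---|---|
| On-site rating at Visit 3, 4 or 5 | that visit | double-blind | yes |
| On-site rating at Visit 6 | that visit | withdrawal | yes |
| Call replacing Visit 3, 4, 5 or 6 | the visit replaced | as for that visit | yes |
| Visit 5 rating after premature discontinuation | Visit 5 | double-blind | yes |
| Rating at an additional or other unscheduled contact | UNS | none | no |
| Rating at Visit 7, if one is made | Visit 7 | none | no |
| Completed suicide | not stated | depends on the form used | only if recorded under Visits 3 to 6 |

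**What omission does to a subject's count.** A subject who also has a scheduled rating in the period stays in the denominator and counts as event-free, unless that scheduled rating picks up the same event. A subject with no scheduled rating in the period leaves both numerator and denominator.

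**Spacing of scheduled ratings.** The first comes at Week 14. The later gaps are 27 − 14 = 13 weeks, 40 − 27 = 13 weeks and 41 − 40 = 1 week. Whether a later rating would recover an event between visits depends on the recall period, which the documents do not give.

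**Other safety sections.** Sections 7.3 and 7.4 include scheduled, re-test and unscheduled assessments unless noted otherwise. Section 7.5 restricts vital-signs summaries to scheduled assessments and says so. Section 7.1 removes unscheduled measurements only when the last double-blind value is determined. Section 7.9 counts events during a period and takes a worst category, so that exclusion does not apply, but the section states no rule of its own.

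**Would assigning every rating by date work?** Section 11.2 defines the periods by date. For a premature discontinuer without an end-of-double-blind visit date, the double-blind period ends at most one day after the last dose, apart from subjects lost to follow-up. The extension to 7 days covers only laboratory tests, ECG and vital signs. Section 7.1 recommends Visit 5 safety assessments within 7 days and gives these subjects no run-out. A Visit 5 C-SSRS on days 2 to 7 now counts as double-blind. Under pure date assignment it would move to safety follow-up, which has no C-SSRS table. Dates should therefore be used only for unscheduled ratings.

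**Weight of one omitted case.** Arm sizes are not given, so n is assumed. The weight is 100 × 1/n percentage points: 1.00 at n = 100, 0.48 at n = 210 and 0.25 at n = 400. This is the weight of a single case, not an estimate of how many are lost.

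**The case against.** The strongest reply is that no route to a lost rating is documented. The addendum's list with the C-SSRS on it is for calls that replace visits, and those are filed under the visit and counted. The separate UNS instruction does not say that a C-SSRS is completed. A reader might infer that the addendum generates unscheduled ratings that the SAP then discards. The documents do not support that, and the full visit schedule is not among them. Nor does any sentence say that unscheduled C-SSRS ratings are dropped. The exclusion follows from a closed list.

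A reader might also infer that a completed suicide can never reach a C-SSRS table. That is not shown. Category 10 is listed for tabulation, and the outcome depends on a recording convention that the documents do not give.

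Nor is suicidality held to a weaker standard overall. Section 7.2 summarizes suicide/self-injury as an AESI after ISB adjudication, with no scheduled-visit restriction and up to 30 days after the end of double-blind treatment. It also summarizes cases sent for adjudication, fatal TEAEs and deaths, with a listing of causes. Section 7.1 has safety data listed.

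These points limit the size of the problem but do not supply the missing rule. AESI tables are by preferred term, not by C-SSRS category, and a listing gives no incidence by arm.

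**Conclusion.** The point holds as a gap in the assignment rule. If Section 7.9 is followed literally, an unscheduled post-baseline C-SSRS rating is left out of the period tables and the shift tables, while unscheduled laboratory and ECG results are included in theirs. Any resulting bias is likely to be downward. Its size cannot be derived, because the number of unscheduled ratings is unknown and may be zero. Each omitted case would weigh about 0.25 to 1.00 percentage points for assumed arms of 400 down to 100. The tables are descriptive, so no hypothesis test is affected, and the events may be visible in other outputs. The conclusion assumes that the visit list is applied as a closed list and that unscheduled ratings are not relabelled to a planned visit during data handling.

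**What to change.** In SAP Section 7.9:

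- Keep the present mapping for Visits 3 to 6, so that a Visit 5 rating after premature discontinuation still counts as double-blind.
- Add that unscheduled post-baseline C-SSRS assessments are assigned by date to the double-blind or treatment withdrawal period under Section 11.2. Give them the same 7-day allowance after premature discontinuation that laboratory, ECG and vital-signs data have.
- State that the worst rating in the period is used, and that these ratings count in the numerator, the denominator and the shift tables.
- State that ratings falling in neither period are listed only.
- For category 10, add a footnote pointing to the AE and death outputs. Merging AE or death records into the table would mix data sources in an output defined by the C-SSRS.

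The cost is SAP wording and one date-based flag, with no new data. The one drawback is that closely monitored subjects contribute more ratings and so have more chances of a positive one. A footnote giving the number of subjects with unscheduled ratings in each arm would let a reader judge this.

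### SAP 7.9 counts C-SSRS at Visits 3 to 5 as double-blind by visit label, although SAP 11.2 places an early stopper's off-drug visits in safety follow-up

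*SAP*

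**What the plan says.** SAP 7.9 sorts C-SSRS assessments by scheduled visit: "V3 (Week 14), V4 (Week 27) and V5 (Week 40) = double-blind study period". Visit 6 goes to the withdrawal period and Visit 1 to none. There is no condition on the date of the last dose. The rule feeds two displays. One is the category table, where "Percentages will be based on the number of subjects with at least one post-baseline C-SSRS" record within the relevant period. The other is the shift table: "Shift from baseline (baseline as defined in Section 11.4) showing any change in suicidal ideation and suicidal behavior, 1) during the double-blind study period". Withdrawal is shown separately. No other period is tabulated.

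SAP Section 2 sends the reader to 11.2 for the definition of study periods. There the double-blind study period of a completer runs to Visit 5. For early stoppers the wording is: "for those who prematurely discontinued double-blind study treatment (i.e., those without an EODBT date), until one day after double-blind study treatment end date". If that last dose was taken after midnight, the period closes on the last-dose day itself. The one extension for early stoppers covers three data types: "laboratory tests, ECG and vital signs) assessment up to 7 days after last drug intake". The time that follows is safety follow-up, which runs "from one day after the end of double-blind study period for those not starting the treatment withdrawal period until the EOS date".

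SAP 7.1 adds: "A subject who prematurely discontinues treatment may continue the planned study visits until EOS, without the run-out period". It also says that their laboratory, ECG and vital-sign data "measured more than 7 days from the last double-blind study treatment intake will be excluded from analyses".

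**The concern.** One term carries two meanings. 11.2 defines the double-blind study period by dates tied to dosing, while 7.9 fills it by visit number. The two agree for a subject who completes treatment. They disagree for one who stops early and still attends Visit 3 or Visit 4.

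Long-term safety is the primary objective, and these tables are where suicidality by dose will be read. A finding made off drug can appear in an active-dose or placebo column as having occurred in the double-blind period, against the SAP's own definition of that label. Because 7.9 tabulates only the double-blind and withdrawal periods, and the withdrawal table is limited to subjects who took run-out placebo, such a record has no other row to go to. Safety data are listed, so the record can be found there, but a reader of the tables cannot tell it apart.

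**Working it through.** The plan gives no figure to reproduce. The check is a comparison of rules with one worked subject.

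**Inputs.** Visit 3 is at Week 14 and Visit 4 at Week 27 (SAP 7.9). The period end and the 7-day extension come from SAP 11.2, the 7-day exclusion from SAP 7.1, and the 30-day window for treatment-emergent AEs from SAP 7.2. End of study (EOS) is 30 days after the last double-blind dose (SAP Section 2).

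**Assumptions.** First dose on Day 1; visits on nominal days (week × 7); last dose on Day 80, taken in the evening; no run-out.

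**Dates.**
- Visit 3 = 14 × 7 = Day 98; Visit 4 = 27 × 7 = Day 189.
- Double-blind period ends (11.2): 80 + 1 = Day 81. Safety follow-up starts on Day 82.
- 7-day window ends: 80 + 7 = Day 87.
- Visit 3 is 98 − 80 = 18 days off drug, 98 − 81 = 17 days past the period end and 98 − 87 = 11 days past the 7-day window.

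**What each rule does with Day 98.**

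| Data from Visit 3 | Rule | Result |
|---|---|---|
| C-SSRS | 7.9 | Double-blind category and shift tables |
| C-SSRS | 11.2 | Safety follow-up |
| Laboratory, ECG, vital signs | 7.1 | Excluded from analyses |
| AE starting that day | 7.2 and 11.2 | Treatment-emergent (Day 98 is before 80 + 30 = Day 110), but outside the double-blind AE table (after Day 81) |

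**How far off drug a record can be.** This depends on EOS for early stoppers, which the documents leave open.
- If EOS is 30 days after the last dose (Section 2), it falls on 80 + 30 = Day 110. Visit 3 takes place and Visit 4 does not. No record is more than 30 days off drug, and none falls outside the treatment-emergent window.
- If planned visits continue on schedule (one reading of 7.1), Visit 4 is 189 − 80 = 109 days off drug and 189 − 110 = 79 days past the treatment-emergent window.

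**Early Visit 5.** 7.1 recommends the Visit 5 safety assessments within 7 days of the last dose. If they are done on Day 84 (84 − 80 = 4 days off drug), the laboratory, ECG and vital-sign data count as double-blind because 84 ≤ 87. Under 11.2 alone the C-SSRS would be safety follow-up because 84 > 81. Under 7.9 it is double-blind. Applying 11.2 unchanged would therefore drop this record from the tables.

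**The case against.** The strongest reply is that 7.9 is a specific rule and 11.2 a general one. The visit-based assignment looks deliberate: the SAP's change history for version 2.0 records a condition of this kind being added. It gives a programmer one clear instruction. It also keeps the early Visit 5 record, a sound choice for suicidality data. All of this stands, and a reader who inferred that the tables cannot be programmed reproducibly would be wrong.

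Nor does the label strictly mean on drug, even in 11.2. For subjects lost to follow-up the EOS date serves as the end of double-blind treatment, and for completers who end on an interruption the period runs to the day before run-out. Those rules are stated openly and need not change.

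The consequence is also limited. The tables are descriptive, the same rule applies in every arm, and suicide/self-injury is separately an adjudicated AE of special interest with a dated window.

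One sentence saying that 7.9 overrides 11.2 would remove the textual conflict. It would still leave off-drug records mixed into the dose columns of a table that serves the primary objective, with nothing to mark them.

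**Conclusion.** The mismatch is real and worth correcting, but it is modest. It concerns only early stoppers who attend Visit 3 or Visit 4 more than 7 days after their last dose. Completers are unaffected, and Visit 5 is less exposed because 7.1 recommends doing it early. The worked dates rest on nominal visit days and an assumed stop day.

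Three stronger readings are tempting, and the documents support none of them.
- **That the tables are biased for or against the drug.** Positive off-drug records would add to the numerator. Negative ones could enlarge the denominator, but only for a subject with no other post-baseline C-SSRS in the period. The direction cannot be derived.
- **That many subjects are affected.** The documents give no discontinuation rate, and 7.1 says only that early stoppers may continue. The range of stop days that could produce such a record says nothing about how many subjects have one.
- **That records months off drug will appear.** This needs the planned-schedule reading. With EOS 30 days after the last dose, the limit is 30 days.

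**What to change.** Reconcile 7.9 with 7.1 and 11.2:

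- **(a)** For premature discontinuers, apply to C-SSRS the 7-day window already used for laboratory tests, ECG and vital signs. An early Visit 5 C-SSRS then counts as double-blind under both sections.
- **(b)** Show discontinuers' C-SSRS records from more than 7 days after the last double-blind dose in a separate off-treatment (safety follow-up) row, with its own denominator, in both the category and shift tables.
- **(c)** Keep an all-visits total in both tables, so that no suicidality record is lost.

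The rules in 11.2 for subjects lost to follow-up and for completers ending on an interruption stay as they are. It would also help to state which EOS applies to early stoppers, since that sets how far off drug the new row can reach.

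Cost: a few sentences in three sections, one date flag in the analysis datasets, and one extra row plus a total per table. The downside is a slightly smaller double-blind denominator if some subjects have only off-drug records.
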